## 4.0 Study Intervention(s)/Interaction(s)

#### 4.1 Description:

Before the intervention, the study design with use of hypothetical scenarios will be explained to the participant. The concept of randomization will be also be explained. The participants will be asked a few questions to assess their understanding of the study design, specifically the hypothetical nature of the scenarios. We will also assess whether they understand the concept of being randomized to see one

website first and then the other. Only those participants that understand the study design will be invited to participate in the intervention and will be randomized. For subjects that are randomized, a survey will be administered verbally to collect demographic information and information about their kidney disease and comorbidities. The functional health literacy and numeracy assessment and health status questionnaire will be completed. Subjects will be stratified by the transplant center site and then block randomized. One group will be shown the existing SRTR website with its existing SRTR report cards and then the website with the new patient-centered AHRQ report cards for kidney transplants. The other group will be shown the two websites in opposite order. Each participant will have at most 30 minutes to view each of the websites. After viewing each website, responses to the intervention will be collected. Sessions where participants are reviewing the websites will be recorded using Zoom. Figure 2 shows the study design whereby subjects will be block randomized once to one of the four groups consisting of 18 subjects each. At the end of the study, the patients will have access to both the websites.

The study interventions can be administered in person on a laptop. During the COVID-19 pandemic, the intervention can be administered remotely via email and zoom. The link to the websites will be sent via encrypted email and the intervention will be recorded via zoom. The recordings for subjects at Hennepin Healthcare will be stored on computers at that site.

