#### **Procedures Involved**

- 5.1 Study Design: This aim will entail an RCT of kidney transplant candidates at HHS transplant centers to evaluate the new report card.
- 5.2 Study Procedures: The study entails assessing knowledge and perceived value of information along with measure of satisfaction with decision-making and decisional conflict. Open-ended questions that provide feedback on the sites will also be collected at the end of the study procedures. This study involves one study visit, approximately 90 minutes in length, to review the two report card websites. This study visit will be done in person or online using Zoom.

The first 5 participants at each site will be enrolled in a vanguard study to optimize the study design. If no change in study design is required, these subjects will be analyzed in the main study.

For consented patients who will be participating in the study remotely, the study team will contact patients via email to confirm the patient's email address. If participants do have their own electronic device with good internet connection, the study team will send a Zoom link for the Zoom testing session to check patient technology and ability to share their screen.

If a participant is willing to participate but has any issues with internet connection or/and missing or inadequate electronic device, the study team will send the participant a study iPad with internet that participant can use for the intervention

5.0

and then to send back to the study team. We will provide detailed instructions on how to use the iPad and Zoom application. The study will also pay for a FedEx pick up from the participants' home to return the iPad to the study team after the completion of the intervention.

When the clinical coordinator confirms good technology connection (through patient personal electronic device or study iPad). The study coordinator will schedule a 90 minute Zoom study visit. A sample script for the day of this study visit is attached.

If a participant prefers a face to-face study visit and this is allowed based on local site guidelines, the study intervention can be administered in the clinic. A study coordinator will help patients to work on study's iPad and record the Zoom session of the visit.

We estimate that the total time for the study visit will be around 90 min. After viewing each website, responses to the intervention will be collected.

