# 11.0 Number of Participants

## 11.1 Number of Participants to be Consented

The table shows the required sample size for ranges of detectable differences and within-person correlation.

						Correlation			
							0.		
		0.0	0.1	0.2	0.3	0.4	5	0.6	
Ī	0.20	107	98	89	79	67	56	45	

Detectable	0.22	90	82	76	66	56	47	38	
Difference	0.24	76	71	64	55	48	40	33	
	0.25	70	66	59	51	44	37	*	
	0.26	66	61	55	48	41	34	*	
	0.28	57	53	46	41	35	30	*	
	0.30	51	45	41	36	32	27	*	

On the conservative side, we will power the study to detect a proportional difference as small as 25% and therefore plan to enroll at 72 subjects for each organ trial. Recruitment will continue until this desired sample size is achieved. Given the low-risk nature of this project, there will be no stoppage rules based on interim analysis for recruitment.

This 72 is in addition to the 130 subjects enrolled in the interviews and focus groups and usability testing. Thus the total enrollment will be 130 + 72 = 202. The 97 subjects already enrolled along with the 50 subjects that can be enrolled in the trial at HCMC, brings the total maximum enrollment to 147 at HCMC.

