#### 12.3 Identification of Potential Participants:

Potential participants will be recruited based on information from their medical record—they must be kidney transplant candidates with either evaluations or waitlisted at the HHS. All potential patients under the care of the Hennepin Healthcare use an EMR that will be accessed to screen for adult patients. During the chart review, patients meeting exclusion criteria will be excluded. All potential transplant candidate participants are patients of the Hennepin Healthcare.

All members of the research team have access to Epic. The research team will run a report for potential participants who meet inclusion/exclusion criteria for the study. An eligibility report may be generated by FileMaker and EPIC that have similar information for kidney transplant candidates.

The study coordinators will create a patient list to evaluate possible participants against inclusion and exclusion criteria. Coordinators will exclude patients who have declined to participate in research, unless this study is presented by the care team and the patient wishes to learn more about the study.

While preparing invitation letters, the study team may review the list to determine if some potential participants are coming into clinic for routine care. If a potential participant is coming into clinic for routine care, the study team may approach the potential participant in clinic.

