#### 17.0 Statistical Considerations

#### 17.1 Data Analysis Plan:

Before initiating outcome analyses, we will perform exploratory analysis to examine frequency distributions for all baseline variables, with particular attention to variable ranges and skewness. We will examine group comparability at baseline between the two RCT arms to assess whether randomization succeeded in creating equivalent groups. These analyses will help determine potential need to incorporate additional covariates in later analyses using propensity-based methods (22-25). Relevant baseline measures include socio-demographic factors, health literacy and numeracy assessment, and baseline survey information.

17.2 Power Analysis: The table shows the required sample size for ranges of detectable differences and within-person correlation.

						Correlation		
							0.	
		0.0	0.1	0.2	0.3	0.4	5	0.6
	0.20	107	98	89	79	67	56	45
Detectable	0.22	90	82	76	66	56	47	38
Difference	0.24	76	71	64	55	48	40	33
	0.25	70	66	59	51	44	37	*
	0.26	66	61	55	48	41	34	*
	0.28	57	53	46	41	35	30	*
	0.30	51	45	41	36	32	27	*

On the conservative side, we will power the study to detect a proportional difference as small as 25% and therefore plan to enroll at 72 subjects. Recruitment will continue until this desired sample size is achieved.

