	☐ I will use University services to access and retrieve records from the Bone Marrow Transplant (BMPT) database, also known as the HSCT (Hematopoietic Stem Cell Transplant) database.
	oxtimes I will pull records directly from EPIC.
	$\square$ I will retrieve record directly from axiUm / MiPACS
	$\square$ I will receive data from the Center for Medicare/Medicaid Services
	$\square$ I will receive a limited data set from another institution
18.3	Explain how you will ensure that only records of patients who have agreed to have their information used for research will be reviewed.

Please see pertinent recruitment and screening sections above. Within EPIC, research team members will first look at a potential participant's "Patient Type" to determine if he or she has opted in or opted out of research. If the potential participant has not opted out of research, preliminary screening will take place prior to the research team approaching the potential participant. If a potential participant has opted out of research, the research team will not look into the chart and will not be able to do preliminary screening. Instead, the researcher will approach the potential participant in person to ascertain interest in the study. If the potential participant expresses interest in the study, the researcher will inform the potential participant that his or her medical record will be reviewed to determine eligibility and ask for the potential participant's permission to view his or her medical record for this purpose.

18.4 Approximate number of records required for review:

There are approximately 300 kidney transplant candidates on the waiting list at at HHS. The records of these candidates will be screened to enroll 50 of the 72 subjects in the RCT

i	n the RCT.
18.5	Please describe how you will communicate with research participants during the course of this research. Check all applicable boxes
	$\hfill\Box$ This research involves record review only. There will be no communication with research participants.
	Communication with research participants will take place in the course of treatment, through MyChart, or other similar forms of communication used with patients receiving treatment.

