## 23.0 **Setting**

23.1 Research Sites:

The research will take place locally at the HHS. Subjects will be recruited from the Hennepin Healthcare Clinic.

- 23.2 International Research: N/A
- 23.3 Community Based Participatory Research: N/A

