#### 24.0 Multi-Site Research

24.1 Study-Wide Number of Participants:

This study is performed at HHS. This site will enroll kidney transplant candidates as subjects for the RCT.

- 24.2 Study-Wide Recruitment Methods: N/A
- 24.3 Study-Wide Recruitment Materials: N/A
- 24.4 Communication Among Sites: N/A

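### Do the 22 trial subjects with no named enrolling site leave the planned sample of 72 in doubt?

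*Combined protocol and SAP*

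**What the plan says.** **Size.** Section 17.2 states: "we will power the study to detect a proportional difference as small as 25% and therefore plan to enroll at 72 subjects". Section 11.1 gives the same figure, and section 4.1 and Figure 2 divide it into four groups of 18. Sections 11.1 and 17.2 both say that recruitment goes on until the target is met.

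**Local share.** Section 18.4 has about 300 waitlisted HHS candidates and continues: "The records of these candidates will be screened to enroll 50 of the 72 subjects in the RCT". Section 11.1 refers to "The 97 subjects already enrolled along with the 50 subjects that can be enrolled in the trial at HCMC", giving a ceiling of 147 there. The same paragraph gives a total enrolment of 130 + 72 = 202.

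**Text that reads as one site.** Section 12.3: "All potential transplant candidate participants are patients of the Hennepin Healthcare". Section 23.1: "The research will take place locally at the HHS". Section 24.1: "This study is performed at HHS. This site will enroll kidney transplant candidates as subjects for the RCT". Sections 24.4 and 24.5 mark communication among and to sites as not applicable.

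**Text that reads as several sites.** Section 4.1: "Subjects will be stratified by the transplant center site and then block randomized". Section 5.2: "The first 5 participants at each site will be enrolled in a vanguard study to optimize the study design". Section 6.1 keeps recordings at the sites concerned, and section 12.2 lists HHS as one that is included. Sections 25.1 and 25.2 make HHS the coordinating center, receiving data from the sites and holding calls with them. Sections 18.7 and 18.11 mention M-Health patients and M-Health documents, but only in connection with storage.

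**The concern.** A reader who adds up the enrolling sites reaches 50, not 72, and finds no sentence that supplies the rest. The sections also disagree on whether there is any site other than HHS. Section 24.1 is the place for a study-wide count and gives none.

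Three things could depend on the answer. If HHS were the only site and its 50 were a true ceiling, the trial would stop short of the number it was sized on. If site is a randomization stratum, the number of strata is unknown. And because the vanguard phase takes five subjects per site, its size is unknown too. The first would be serious: a trial that could never reach its own target would need a new power statement.

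**Working it through.** **1. Reproduce the plan's counts.**

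- Four groups of 18 (section 4.1): 4 × 18 = 72.
- Two website orders of 36 (Figure 2): 36 + 36 = 72.
- Local ceiling (section 11.1): 97 + 50 = 147.
- Study-wide total (section 11.1): 130 + 72 = 202.

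All four agree with the text.

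**2. The unassigned remainder.** 72 − 50 = 22, and 22/72 = 30.6%.

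**3. Could HHS take them all?** HCMC is not in the abbreviation list. Treating it as HHS is an inference, supported by both carrying the figure 50. On that reading 97 + 72 = 169, which exceeds 147 by exactly 22. So the 22 are not meant to come from HHS under this ceiling.

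**4. Does the document point to another source?** Section 11.1 sets two totals side by side:

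| Component | Total enrolment | HCMC | Difference |
|---|---|---|---|
| Interviews, focus groups, usability testing | 130 | 97 | 33 |
| Randomized trial | 72 | 50 | 22 |
| Sum | 202 | 147 | 55 |

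Both components are larger in the first column, and 33 + 22 = 55. That is the pattern of a study-wide count next to one site's share. Section 18.4 makes the same split by calling the 50 a part of the 72. The M-Health references in sections 18.7 and 18.11 imply participants elsewhere. This supports the reading but does not prove it: section 1.1 gives the 97 without calling it a local figure, and no sentence assigns the 22 to M-Health.

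**5. Does any statistical quantity depend on which site enrols them?**

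- *Sample size.* The table in sections 11.1 and 17.2 is indexed by detectable difference and within-person correlation only. For a difference of 0.25 it requires 70, 66, 59, 51, 44 and 37 at correlations 0.0 to 0.5. The planned 72 covers the largest of these, since 72 ≥ 70. The number of sites is not an input.
- *Analysis.* Section 17.3 specifies a chi-square test and logistic regressions and names no site term. Every subject views both websites, so a within-person comparison is made inside one site however many sites there are.
- *Strata.* With one site, stratifying by site does nothing. With two, it balances order within each. The procedure in section 4.1 works either way.
- *Vanguard.* One site gives 5 subjects and two give 10. If the design is unchanged they are analysed in the main study (section 5.2), so the total is 72 in both cases.

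**The case for a change.** The strongest case for acting is that this is not merely a site's local paperwork. It names HHS as the coordinating center, has a study-wide section, and makes the center responsible for passing amendments to all participating centers, so it ought to name them. Sections 12.3 and 24.1 also fit the local-version reading poorly, because they are worded as if they covered every participant. And if the single-site wording were taken literally, 50 subjects would fall below the table's 70, 66, 59 and 51 for a 0.25 difference at correlations 0.0 to 0.3. They would suffice only from 0.4, where it asks for 44.

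The contradiction in wording stands. The plural reference to HHS transplant centers in sections 1.1 and 5.1 could explain the site strata without an outside partner, but it does not place the 22, because section 18.4 gives its 50 for HHS as a whole. The number of vanguard subjects would matter if the design changed after that phase, since 5 or 10 people would then be outside the provision for analysing them in the main study. That number would be known from the enrolment log by then.

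The power argument does not stand. The plan nowhere limits the trial to 50. It says that recruitment continues to 72, and the sentence giving the 50 describes it as part of that 72. A shortfall calculation at 50 describes a trial that is not planned.

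**Conclusion.** The 22 subjects (30.6% of the trial) do lack a named enrolling site, and the single-site and multi-site sections do not agree. The likely cause is incomplete editing of a multi-site protocol into an HHS version. This is a clerical gap, and the trial team can settle it from its own site list.

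Nothing in the design or the results turns on it. The target stays at 72, the sample-size table applies as written, and the chi-square and logistic analyses are the same whoever enrols the remaining subjects. Naming the partner would be housekeeping, so no change to the plan follows.

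This rests on three assumptions: that HCMC and HHS are the same institution, that another site (plausibly M-Health) supplies the 22, and that recruitment runs to 72 as sections 11.1 and 17.2 say. If the trial were in fact closed at 50, the third would fail and the conclusion would need another look, but no section plans that.

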## 19.0 **Confidentiality**

19.1 Data Security:

Data will be maintained in paper, digital, and audio formats. Electronic data from the de-identified paper forms will be stored on a secure server at HHRI. All servers have encryption and require users to log-in with usernames and passwords. Paper data will be stored in filing cabinets in the researchers' locked offices. Electronic locations for data storage, analysis and sharing: HHRI secure server.

## 20.0 Provisions to Monitor the Data to Ensure the Safety of Participants

20.1 Data Integrity Monitoring.

This is a minimal risk project, collecting quantitative and qualitative data from interviews. The principal investigator will be responsible for overseeing the data integrity throughout the project.

20.2 Data Safety Monitoring. N/A – this research involves no more than minimal risk

#### 21.0 Compensation for Research-Related Injury

- 21.1 Compensation for Research-Related Injury: N/A minimal risk.
- 21.2 Contract Language: N/A

#### 22.0 Consent Process

22.1 Consent Process (when consent will be obtained):

Potential participants will be approached either in clinic, via mailing followed by a phone call from study personnel, or encrypted email (see section 12.1). At the time of approach, participants will be given a consent form for review. Patients will be consented either in person, by phone, or electronically using REDCap HHRI.

Participants consented by phone will mail their signed consent form back to the study team. Participants will be given a copy of the consent form for their records.

All potential participants will be given time to think about the study information presented to them. They will be encouraged to ask questions and discuss the study with individuals other than the study personnel. Subjects will have adequate time to review the consent form and ask questions before signing the consent form. Subjects will be informed of the voluntary nature of the study. The individual presenting the study will stress the fact that the subject's care and/or relationships with the HHS will not be affected by the subject's decision to participate or not to participate.

- 22.2 Waiver or Alteration of Consent Process (when consent will not be obtained, required information will not be disclosed, or the research involves deception): N/A
- 22.3 Waiver of Written/Signed Documentation of Consent (when written/signed consent will not be obtained): NA
- 22.4 Non-English Speaking Participants: N/A
- 22.5 Participants Who Are Not Yet Adults (infants, children, teenagers under 18 years of age): N/A
- 22.6 Cognitively Impaired Adults, or adults with fluctuating or diminished capacity to consent: N/A
- 22.7 Adults Unable to Consent: N/A

## 23.0 **Setting**

23.1 Research Sites:

The research will take place locally at the HHS. Subjects will be recruited from the Hennepin Healthcare Clinic.

- 23.2 International Research: N/A
- 23.3 Community Based Participatory Research: N/A

#### 24.0 Multi-Site Research

24.1 Study-Wide Number of Participants:

This study is performed at HHS. This site will enroll kidney transplant candidates as subjects for the RCT.

- 24.2 Study-Wide Recruitment Methods: N/A
- 24.3 Study-Wide Recruitment Materials: N/A
- 24.4 Communication Among Sites: N/A

24.5 Communication to Sites: N/A

#### 25.0 Coordinating Center Research

HHS is Coordinating Center for this research study.

- 25.1 Role: The data coordinating center will be involved in receiving de-identified data from each of the sites and doing the final analysis.
- 25.2 Responsibilities: The data coordinating center will hold regular calls with the coordinators at each site to ensure that proper procedures are used. During these calls, the coordinating center will ensure that the most current version of the protocol is being followed and that amendments to the protocol are communicated to all centers.
- 25.3 Oversight: Provide each participating center FWA number with OHRP (if the research is federally funded). The protocol events at HHS will be reported to the IRB at HHS.
- 25.4 Collection and Management of Data: The data will be collected in a central data collection tool such as RedCap with no identifiers. The identifiers will be maintained at the individual study site only. The de-identified data will be used for analysis.

#### 26.0 Resources Available

#### 26.1 Resources Available:

To assist with this study, the study will utilize services from Hennepin Healthcare Research Institute.

HHS will provide regulatory and clinical coordinator support for the study for subjects enrolled at HHS.

